9 PARTICIPANT REIMBURSEMENT

Participants will be compensated with a \$10 gift card for the pre-test assessment and a \$10 gift card for the intervention and immediate post-test assessment.

10 MEASURES

10.1 Participant Characteristics. Demographic data will be collected on participant gender, age, race/ethnicity, sexual orientation, and receipt of free or reduced-price lunch (a proxy for socioeconomic status). Sexual activity status will be assessed with two items: one that inquired if participants had ever engaged in any sexual activity, including sexual touching, oral sex, and/or intercourse; and a second, if they answered “yes” to the first question, that inquired if participants had ever engaged in sexual intercourse. Additionally, among those who reported sexual intercourse, information was gathered about condom use at last sex.

10.2 Program Acceptability. Program acceptability will be assessed through a questionnaire that was adapted from prior acceptability surveys (Bauermeister et al., 2015; Widman et al., 2017). Specifically, six items will be included to assess six aspects of acceptability: 1) how much participants liked the program; 2) how much they learned from the program; 3) how much they felt the program kept their attention; 4) whether they would use information from the program in the future; 5) whether the program would be useful for girls their age; and 6) whether the program would be useful for boys their age. Items are rated on a four-point Likert scale ranging from 0 (*not at all*) to 3 (*a lot*).

10.2 Intentions. Intentions to discuss sexual health and to use condoms will be assessed with two items. The first asks how likely teens are to discuss sexual health issues, including pregnancy and STDs, with their partner(s) prior to sexual activity (communication intentions). The other item asks how likely teens are to use condoms the next time they have sex (condom intentions). Participants will be prompted to answer these questions whether or not they had engaged in sexual activity before. Response options range from 0 (*not at all likely*) to 4 (*very likely*).

10.2 Sexual Self-Efficacy. The Self-Efficacy for HIV Prevention Scale (Brown et al., 2014) will be used to assess self-efficacy about communication and condom use. Six items assess confidence communicating about sexual topics (e.g., “How sure are you that you could talk to your partner about safer sex?”). Two items assess confidence obtaining and using condoms (e.g., “How sure are you that you could have condoms available when you need them?”). Participants responded from 1 (*Couldn't do it*) to 4 (*Very Sure*), with higher scores indicating greater sexual self-efficacy.

10.3 Knowledge. HIV/STD knowledge will be assessed with 9 items (e.g., “STDs usually have noticeable symptoms, like itching or burning”). Participants rate each item as *True*, *False*, or *Don't Know*. Responses are recoded as 0 (*Incorrect or Don't Know*) or 1 (*Correct*). Scores are summed to reflect the total number of correct HIV/STD knowledge questions (possible range=0-9).

10.4 Condom Attitudes. Participants' attitudes about condoms will be assessed with the 3-item effect on sexual experiences subscale of the Condom Attitudes Scale Adolescent Version (St. Lawrence et al., 1994). An example item includes, “Condoms take away the pleasure of sex.” Responses are on a scale from 1 (*Strongly Disagree*) to 5 (*Strongly Agree*).

10.5 Condom Norms. The 3-item condom norm subscale from the Sexual Risk Behavior Beliefs and Self-Efficacy Scale for adolescents (Basen-Engquist et al., 1999) will be used to assess participants' perceptions of their peers' views of condom use. Participants respond from 1 (*Strongly Disagree*) to 5 (*Strongly Agree*) to items such as, “Most teenagers believe condoms should always be used if a person my age has sex”.

10.6 Sexual Assertiveness. Self-reported sexual assertiveness will be assessed with 3-items from the Multidimensional Sexual Self-Concept Scale (Snell, 1998). Items such as, “I’m very assertive about the sexual aspects of my life,” are rated on a scale from 1 (*Strongly Disagree*) to 5 (*Strongly Agree*).

11 STATISTICAL ANALYSIS STRATEGY

11.1 Analysis Plan

First, descriptive statistics will be utilized to summarize sociodemographic variables and pre-test levels of each outcome variable. To establish pre-test equivalence, differences between groups will be assessed using *t*-tests for continuous variables and χ^2 -tests for categorical variables. Second, to assess the efficacy of the HEART intervention from pre-test to immediate post-test, linear regression analyses will be utilized to compute adjusted means and mean differences between intervention and control groups. For each outcome, the corresponding pre-test measure will be included as a covariate. Third, moderation analyses will be conducted to examine if intervention effects are moderated by gender or sexual orientation. Cohen’s *d* value will be calculated as an indication of effect size. Analyses will be completed using SPSS Version 24.

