4.2 Study Population

All 10th and 11th grade students from a school district in the southeastern U.S. will be recruited to participation in this study (n recruited = 754).

4.2.1 *Inclusion Criteria*

1. Must be a 10th or 11th grade student
2. Must speak English
3. Provide written parental consent
4. Provide written student assent

4.2.2 *Exclusion Criteria*

1. Unable to speak fluent English
2. Unwilling or unable to provide parent consent or student assent

5 **QUALTRICS DATA COLLECTION**

All data collected will be directly entered and stored in the web-based Qualtrics research electronic data system. This Qualtrics database will be stored, maintained, and monitored by the NC State Office of Information Technology and the study personnel. The Qualtrics system is a secure, web-based application designed to support survey and data collection. NC State has a license to host the Qualtrics system. Access to the Qualtrics database will be carefully restricted to authorized research team members as needed to perform their job functions, pursuant to Federal regulations.

6 **RECRUITMENT**

Potential study participants will be recruited via in-class announcements at their high school. Students will be provided with an informed consent document to take home to their parent/guardian. Parents are asked to sign and return the form to indicate whether child is approved to participate in the study. All students in the 10th and 11th grades will be recruited.

7 **INFORMED CONSENT**

Written informed consent from parents will be collected via an IRB-approved informed consent document. Once parental consent is collected, study staff will explain the study to students and also provide them with a written assent form approved by the NC State IRB. Students will be allowed sufficient time to ask questions about the study and express understanding. Only students who have received parental consent and have signed an assent document will be allowed to participate in the study. Written consent/assent documentation will be stored in a secure physical or electronic server location according to standard operations approved by the NC State IRB.

8 **DATA COLLECTION PROCEDURES**

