After parental consent and student assent are obtained, pre-test data will be collected using computerized Qualtrics surveys in a small group classroom setting. Participants will then be randomly assigned to either the HEART for Teens online program or to an attention-matched control program focused on cultivating academic growth mindsets, called Growing Minds (Burnette, Russell, Hoyt, Orvidas, & Widman, 2017). Random assignment to study condition will be conducted using random sampling and allocation procedures in SPSS version 24. Participants will be stratified based on sexual activity status (ever sexually active versus never sexually active). Approximately one week after pre-test, participants will complete the online intervention on a study-provided netbook computer as well as a computerized Qualtrics post-test survey in a small group classroom setting. Participants will use headphones to listen to program content and to control for any outside noise.

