11.2 Sample Size Considerations

For this preliminary assessment, the final sample size will be determined by the number of students and parents who granted consent.

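### The efficacy regressions do not name the randomisation stratum as a covariate; secondarily, difference tests with no margin cannot establish baseline equivalence

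*Combined protocol and SAP*

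**What the plan says.** **Randomisation.** Section 8 (Data Collection Procedures) places allocation after the pre-test: "Participants will then be randomly assigned to either the HEART for Teens online program or to an attention-matched control program". It then says: "Participants will be stratified based on sexual activity status (ever sexually active versus never sexually active". The method is given only as random sampling and allocation procedures in SPSS. Neither an allocation ratio nor a device for balance within strata, such as blocking, is described.

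**Efficacy model.** Section 11.1 plans linear regressions giving adjusted means and mean differences. On covariates it says: "For each outcome, the corresponding pre-test measure will be included as a covariate". No other covariate is named for these models. Gender and sexual orientation appear only as moderators, in a later step.

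**Baseline comparison.** After a sentence planning descriptive statistics, Section 11.1 continues: "To establish pre-test equivalence, differences between groups will be assessed using" t-tests for continuous variables and chi-square tests for categorical ones. No significance level, margin, confidence-interval criterion or equivalence procedure is given.

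**Sample size.** Section 4.2 gives "n recruited = 754" for all students in the two grades. Under Section 11.2, "the final sample size will be determined by the number of students and parents who granted consent".

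**The concern.** An analysis should normally reflect the factor used to restrict the randomisation. When allocation is balanced within strata, the design removes the between-stratum part of the chance difference between arms. A model without the stratum still counts that part as noise, so its intervals are somewhat too wide and its tests somewhat conservative. When allocation is not balanced within strata, the stratum is simply a baseline variable that may predict the outcome, and leaving it out gives up some precision. Past sexual activity could plausibly relate to intentions, self-efficacy and assertiveness beyond the pre-test score, although the plan gives no correlations.

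The baseline sentence has a different fault: its purpose and its method do not match. Tests whose null hypothesis is no difference cannot, by failing to reject it, establish that the arms are equivalent. Because the sample is whoever consents, the gap that would pass as non-significant is not fixed in advance. At stake is what the report may say about baseline comparability, not the efficacy result.

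**Working it through.** The plan states no alpha, power, SD, margin or target sample size, so there is no figure of its own to reproduce. What follows is illustrative.

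**A. Leaving out the stratum**

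Inputs: stratified randomisation (Section 8) and the pre-test value as the named covariate (Section 11.1). Assumptions: two-sided 5% test, large samples, no clustering, and a partial correlation *r* between stratum and post-test given pre-test of 0.1, 0.2 or 0.3.

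1. *Balanced within strata, stratum and pre-test uncorrelated.* Model SE / true SE = 1/√(1 − r²), and true type I error = 2[1 − Φ(1.96/√(1 − r²))].

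| r | 1 − r² | SE ratio | SE too large by | Type I error |
|---|---|---|---|---|
| 0.1 | 0.99 | 1.005 | 0.5% | 0.0489 |
| 0.2 | 0.96 | 1.021 | 2.1% | 0.0455 |
| 0.3 | 0.91 | 1.048 | 4.8% | 0.0399 |

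2. *Balanced within strata, stratum and pre-test correlated at c.* The ratio becomes 1/√(1 − r²(1 − c²)), which is smaller. For r = 0.3 and an assumed c = 0.5: 1 − 0.09 × 0.75 = 0.9325, and 1/√0.9325 = 1.036. The standard error is then 3.6% too large and the type I error is 2[1 − Φ(1.96 × 1.036)] = 0.042. The figures in the table are therefore upper bounds for each r.

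3. *Not balanced within strata.* The standard errors without the stratum are valid. Adding it multiplies them by √(1 − r²) = 0.995, 0.980 or 0.954, a gain of 0.5%, 2.0% or 4.6%.

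**B. What a non-significant baseline test allows**

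Inputs: 754 students as the ceiling (Section 4.2) and no target (Section 11.2). Assumptions: 1:1 allocation, two-sided 5% test, no clustering, totals of 200, 400 or 754.

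The largest non-significant observed gap, in SD units, is 1.96 × √(2/(N/2)) = 3.92/√N:

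- N = 200: 3.92/14.14 = 0.277
- N = 400: 3.92/20.00 = 0.196
- N = 754: 3.92/27.46 = 0.143

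The same result, not significant, thus covers a gap about twice as large at 200 students as at 754. On the same assumptions, a true difference of 0.2 SD would be missed with probability 71% at N = 200 and 22% at N = 754.

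A formal equivalence test is not an easy substitute. For an assumed margin of 0.2 SD, two one-sided 5% tests, 80% power and a true difference of zero, n per arm = 2 × ((1.645 + 1.282)/0.2)², about 429. That is 858 in total, more than the 754 students approached.

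**The case against.** **On the stratum.** The gain is small and conditional. Balance within strata is not stated, the correlations are assumed, and Section 11.1 does not say that the pre-test value is the *only* covariate. All of this stands, which is why the point is an improvement and not an error that threatens the result. The cost is also small, and the present silence leaves the model open to choice after the data are seen. A further objection is that Section 15.1 lets students skip any item, so an adjusted model might lose cases. This does not stand if the covariate is the stratum as randomised: a student who was allocated within a stratum has one.

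**On the baseline sentence.** It can be read as an ordinary comparability check. The plan sets no rule turning a non-significant result into a declaration of equivalence, and the preceding sentence already plans descriptive statistics. This limits the point to wording and reporting. It does not remove it, because the tests are given a purpose beyond description that they cannot serve.

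**Stronger readings that a reader might infer.** One is that unproven baseline equivalence weakens the efficacy comparison. The documents do not support this: no later step uses the test results, and baseline comparability rests on randomisation. Adjustment for the pre-test value adds precision and allows for chance imbalance in that measure; it is not what makes the comparison unbiased. Another is that leaving out the stratum invalidates the tests or inflates false positives. The working shows valid or slightly conservative tests. A third is the chance of at least one significant baseline result under proper randomisation: 1 − 0.95¹² = 46% for 12 independent tests, rising to 56% for 16. That describes false alarms, not unsupported reassurance, and depends on how the variables are counted, so the point does not rest on it.

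**Conclusion.** Both parts hold and both are minor.

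The main part is that the efficacy regressions should name the stratification factor. With balance within strata, the cost of leaving it out is a standard error too large by at most about 5% at the largest correlation assumed here, and less if stratum and pre-test are related. Without balance, the cost is a similarly modest loss of precision. There is no bias in either case, and no inflation of type I error.

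The secondary part, that the planned tests cannot establish equivalence, is a matter of logic and does not depend on the figures. It affects only what could be concluded about baseline. The claim that these tests introduce no bias is confined to the tests themselves; it says nothing about other sources of bias, such as loss between the pre-test and the session about a week later.

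**What to change.** **Main change, Section 11.1.** Replace the covariate sentence with: *Each outcome will be regressed on arm, its own pre-test value and the sexual-activity stratum as randomised.* The cost is 1 degree of freedom per regression. The item is already collected at pre-test, so no new data are needed. It would help to state in Section 8 whether allocation is balanced within strata, since this decides which case in the working applies.

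**Secondary change, Section 11.1.** Replace the baseline sentence with: *Pre-test characteristics and outcomes will be tabulated by arm for all randomised students, with standardised differences; no claim of equivalence will be made on the basis of significance tests.* The cost is one sentence and a column of standardised differences in the baseline table.

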15 PATIENT SAFETY AND MONITORING PLAN (PSMP)

15.1 Risks of Study Participation

The psychological risks directly posed by participating in this study are judged to be minimal and rare (<1%). One risk of participating in this study is that participants may feel uncomfortable answering sensitive questions about their attitudes or private/illegal behaviors (e.g., sexual activity). To reduce this risk, we will inform students that they do not have to answer any questions that they do not want to answer. They will be told that they can skip any items that make them uncomfortable or stop their participation at any time. Participants can also speak with members of the research team if they become upset, and/or the research team can provide students with referrals if they would like to speak with someone about any of the information they receives as part of this program.

Another risk of participating is that the data we are collecting is sensitive and must be carefully protected to ensure confidentiality. Several steps will be taken to protect participant survey data and academic records. This includes deidentifying all data by using only a participant ID number, and not the participant's name. We will also store data in password-protected files on our secure server. The spreadsheet linking participant names with ID numbers will be stored in a separate file from participant data and secured with a separate password. Only the PI, Co-Investigator, and Project Manager will have access to this spreadsheet.

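### Does the lack of a rule for missing pre-test scores undermine the efficacy regressions?

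*Combined protocol and SAP*

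**What the plan says.** Section 11.1 states that "linear regression analyses will be utilized to compute adjusted means and mean differences between intervention and control groups", and then "For each outcome, the corresponding pre-test measure will be included as a covariate". It names no analysis set and no method for missing values.

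Section 15.1 says that "we will inform students that they do not have to answer any questions that they do not want to answer" and "They will be told that they can skip any items that make them uncomfortable or stop their participation at any time".

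Section 8 places the pre-test first; after it, "Participants will then be randomly assigned to either the HEART for Teens online program or to an attention-matched control program". Neither the eligibility list in section 4.2 nor section 8 requires a complete pre-test.

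On scoring, section 10 says "Intentions to discuss sexual health and to use condoms will be assessed with two items", so each intention outcome is one question. Section 10.3 says of knowledge that "Scores are summed to reflect the total number of correct HIV/STD knowledge questions (possible range=0-9"). Self-efficacy has six communication items and two condom items. Attitudes, norms and assertiveness have three items each. No rule is given for a partly answered scale.

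**The concern.** An ordinary linear regression cannot use a record with a missing covariate. The items concern sex, condoms and STDs, and students are told that they may leave them blank, so some blanks are to be expected. Read literally, the plan discards observed post-test outcomes because of a gap in a baseline variable. The number analysed may then differ between outcomes.

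Three things would be at stake. The first is precision, in a trial whose size is set by consent (section 11.2), so lost students cannot be replaced. The second is clarity about which students each estimate describes. The third is freedom to choose, after seeing the data, whether to prorate a scale or void it.

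**Working it through.** The plan gives no skip rate, power, alpha or pre-post correlation, so it has no figure to reproduce. Skip rates and correlations below are assumptions.

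**Step 1. Can the loss bias the arm comparison?** Under section 8 the pre-test is completed before allocation. Whether a pre-test score is missing is therefore a baseline characteristic, balanced in expectation. Restricting to students with a pre-test score leaves a randomised comparison within a subgroup defined before allocation. The estimate departs from the effect in all students only if the effect differs among those who skipped. As an extreme case, take an effect of 0.30 among answerers and none among skippers. With 2% skipping, the all-student effect is 0.98 × 0.30 = 0.294, against 0.30 in complete cases.

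**Step 2. How large is the certain loss?** With item skip rate s and k items that must all be answered, skips being independent, the fraction kept is f = (1 − s)^k. The standard error rises by 1/√f − 1. For a single-item intention outcome, k = 1:

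| s | students lost | rise in SE |
|---|---|---|
| 0.5% | 0.5% | 1/√0.995 − 1 = 0.3% |
| 1% | 1.0% | 1/√0.99 − 1 = 0.5% |
| 2% | 2.0% | 1/√0.98 − 1 = 1.0% |
| 5% | 5.0% | 1/√0.95 − 1 = 2.6% |

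As an illustration, assume 200 students per arm and a standardised difference of 0.3 without covariate adjustment. Power falls from 0.851 to 0.847 at 1% and to 0.844 at 2%.

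**Step 3. What if any skip voids a scale?** The plan does not say that it does. If it did:

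| Scale | lost at s = 0.5%, 1%, 2% | rise in SE |
|---|---|---|
| 3 items (attitudes, norms, assertiveness) | 1.5%, 3.0%, 5.9% | 0.8%, 1.5%, 3.1% |
| 8 items (self-efficacy, if one scale) | 3.9%, 7.7%, 14.9% | 2.0%, 4.1%, 8.4% |

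If self-efficacy is scored as separate six-item and two-item parts, the losses at s = 1% are 5.9% and 2.0%. Skips concentrated in the same students also give smaller losses. Knowledge is a count of correct answers, so a score exists after a skip and voiding does not naturally apply.

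**Step 4. Would the simple remedy do better?** For outcome variance 1 and pre-post correlation r, the variance of the arm effect is proportional to (1 − r²)/f for complete cases, 1 − f·r² for mean fill with a missing indicator, and 1 − r² with nothing missing. Mean fill is better only when r² < 1/(1 + f). That threshold is r = 0.711 at f = 0.98 and 0.735 at f = 0.851.

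For the 8-item scale at s = 1%, f = 0.923 and complete cases cost 4.1% in SE:

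- r = 0.5: √[(1 − 0.923 × 0.25)/0.75] − 1 = 1.3%
- r = 0.7: √[(1 − 0.923 × 0.49)/0.51] − 1 = 3.6%
- r = 0.8: √[(1 − 0.923 × 0.64)/0.36] − 1 = 6.6%

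For a single item at s = 1%, mean fill costs 0.2% at r = 0.5 and 0.9% at r = 0.8, against 0.5% for complete cases. The same instruments are repeated about one week apart (section 8), so a high correlation is plausible, though the documents give none.

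**The case for a change.** The strongest case for a change is that the omission is plain, the questions are sensitive, and a few lines of text would close it. That much is correct: no section supplies a missing-covariate rule, a partial-scale rule or an analysis set. The review of completeness in section 14 is monitoring and does not settle how the data are analysed.

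The losses also need not be small. At a 5% skip rate with every skip voiding the score, an 8-item scale would lose 1 − 0.95^8 = 33.7% of students. That figure stacks a high skip rate, independent skips, and a scoring rule that the plan never adopts. An analyst facing such a loss would ordinarily average the answered items. A choice left until after the data are seen does leave some latitude, and that part of the objection stands. Its effect on the arm comparison is limited, because baseline blanks do not depend on arm.

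Missing post-test scores are the more serious possibility, since they could differ by arm, and they have no rule either. No handling of the pre-test covariate would cure that, so it does not strengthen this point.

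**Conclusion.** The gap is real but minor, and no change to the plan follows. As written, the regressions still give a valid randomised comparison for students with a pre-test score. The certain cost falls on the two intention outcomes: 0.5% to 2% of students and 0.3% to 1.0% in SE, at assumed skip rates of 0.5% to 2%. Larger costs depend on one skip voiding a scale, and an analyst can avoid them by ordinary scoring practice. The simple covariate fill is not clearly better, since it gains or loses precision according to a correlation that the documents do not give. For a trial described as a preliminary assessment (section 11.2), this is detail that analysts can be expected to fill sensibly.

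The conclusion rests on two assumptions: the pre-test is completed before allocation, as section 8 states, and skipping of single items is uncommon. It does not extend to missing post-test scores.

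### A modest, nearly free gain in precision: the two single-item intention models adjust only for their own pre-test item, although related scales measured before assignment, and the randomisation stratum, are available

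*Combined protocol and SAP*

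**What the plan says.** Section 11.1 plans that "linear regression analyses will be utilized to compute adjusted means and mean differences between intervention and control groups", and adds: "For each outcome, the corresponding pre-test measure will be included as a covariate". That is the whole covariate list for the main efficacy models. Gender and sexual orientation appear in 11.1 only as moderators, in a later step.

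On the intention outcomes, section 10 says: "Intentions to discuss sexual health and to use condoms will be assessed with two items". One item is for communication and one for condoms, each scored 0 to 4, so each outcome is a single item and so is its pre-test covariate.

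Section 10 also lists related measures:

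- Communication self-efficacy: "Six items assess confidence communicating about sexual topics".
- Condom self-efficacy: "Two items assess confidence obtaining and using condoms".
- Condom attitudes: "attitudes about condoms will be assessed with the 3-item effect on sexual experiences subscale".
- Condom norms: "The 3-item condom norm subscale".
- Assertiveness: "Self-reported sexual assertiveness will be assessed with 3-items".

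Section 11.1 summarises pre-test levels of every outcome, so these scores exist at baseline, and section 8 places the pre-test before random assignment. Section 8 also stratifies the randomisation by sexual activity status (ever versus never), which 11.1 does not name as a covariate. Section 11.2 lets consent determine the sample size.

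**The concern.** A single item usually carries more measurement error than a scale, so the pre-test item may explain only part of the predictable variation in the post-test item. Scales that address the same behaviour, measured at the same sitting, could explain some of the rest. They are recorded before assignment, so adjusting for them cannot introduce post-treatment bias.

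What is at stake is the width of the confidence intervals for two outcomes. The plan has no power calculation and cannot buy precision with more students, so the analysis is the place to look for it. A fixed covariate list would also remove any temptation to choose covariates after the planned baseline significance tests.

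**Working it through.** **Inputs.** The documents state no sample size, alpha, standard deviation, reliability or correlation, so there is no figure of the plan's own to reproduce. The 754 in section 4.2 counts students approached and is only an upper bound on N. Everything below is assumed:

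- *a*, the item's own pre/post correlation: 0.45 to 0.6
- *b*, scale with the pre-test item: 0.25 to 0.45
- *c*, scale with the post-test item: 0.25 to 0.45
- correlation among scales: 0.3

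**Formula, one added scale.** R² = (a² + c² − 2abc)/(1 − b²). The SE ratio is √[(1 − R²)/(1 − a²)], and the equivalent gain in N is (1 − a²)/(1 − R²) − 1.

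**Three added scales with equal correlations.** These act as one composite with variance (1 + 2 × 0.3)/3 = 0.533. Multiply *b* and *c* by 1/√0.533 = 1.369 and use the same formula.

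**Central example, a = 0.5, b = c = 0.35.**

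- Own item only: R² = 0.250.
- One scale: (0.25 + 0.1225 − 0.1225)/0.8775 = 0.285. SE ratio √(0.715/0.75) = 0.976, so the SE is 2.4% smaller, equivalent to about 5% more students.
- Three scales: *b* and *c* become 0.479, and R² = 0.25/0.770 = 0.325. SE ratio √(0.675/0.75) = 0.949, so the SE is 5.1% smaller, equivalent to about 11% more students.

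**Letting b and c differ.** The post-test item comes about a week after the pre-test and follows the programme, so *c* may well be below *b*.

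| a | b | c | SE reduction, one scale | SE reduction, three scales |
|---|---|---|---|---|
| 0.5 | 0.35 | 0.35 | 2.4% | 5.1% |
| 0.5 | 0.35 | 0.30 | 1.2% | 2.6% |
| 0.5 | 0.35 | 0.25 | 0.4% | 0.9% |
| 0.6 | 0.45 | 0.25 | 0.0% | 0.1% |
| 0.45 | 0.45 | 0.45 | 4.9% | 12.4% |
| 0.45 | 0.25 | 0.45 | 7.9% | 16.5% |

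The gain is exactly zero when c = ab, for example 0.27 = 0.6 × 0.45. The last two rows need each scale to predict the post-test item as well as the item's own pre-test does.

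**Cross-check with a measurement-error model, one scale.** Assume item reliability 0.5-0.8, scale reliability 0.8, latent stability 0.9-1.0 and latent correlation 0.3-0.7. The SE falls by 0.2% to 4.1%, equivalent to 0.4% to 8.8% more students.

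**What this means for power.** Assume N = 300, 1:1 allocation, two-sided 0.05, d = 0.25 and a = 0.5. Residual-variance ratios of 1, 0.95 and 0.90 give power of 70.5%, 72.7% and 75.0%. The difference detectable with 80% power moves from 0.280 to 0.273 to 0.266 SD. The ratios 0.95 and 0.90 correspond to SEs 2.5% and 5.1% smaller (√0.95 = 0.975, √0.90 = 0.949).

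**Cost.** One degree of freedom per covariate raises the variance by about 1/(N − 3): 0.5% at N = 200, 0.3% at N = 300 and 0.1% at N = 754. Three scales at N = 300 therefore cost about 1.0% in variance, against a gain equivalent to 1.9% more students in the third row of the table and 11% in the first.

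**The case against.** The strongest reply is that nothing here is an error. Linear regression on the own pre-test score is a standard, unbiased analysis, and sections 3 and 11.2 describe the work as preliminary. That stands, and this is an optional refinement.

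The reply continues that the benefit is speculative. That stands in part. No correlation is documented, the gain can be close to zero, and noise in the single-item post-test score limits what any covariate can achieve. Under the central assumptions the gain still exceeds the cost in degrees of freedom. At the bottom of the range, in a small sample, the two roughly cancel.

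A reader might infer that the related scales and gender go unused. The documents do not support that. Each scale's pre-test score enters its own outcome's model and the baseline comparison, and gender is a planned moderator. The scales are absent only from the two intention models, and gender only from the main efficacy models.

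A reader might also infer that every efficacy model would gain, or that the equivalent of 11% more students is on offer generally. That figure needs three scales and equal correlations with both the pre-test and post-test items, so it could apply only to condom intention. No gain was calculated for the other outcomes or for gender.

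Finally, section 15.1 lets students skip any item, and the plan has no missing-data rule. Under complete-case analysis, added scales could lose a few percent of students and cancel the gain. This stands, so the change needs a rule that also covers the outcome's own pre-test score.

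**Conclusion.** The point holds as a minor improvement. The intention models in 11.1 adjust for a single pre-test item, and closely related scores measured before assignment are available but not in those models. Over the assumed correlations one added scale shrinks the standard error by about 0% to 8% and three by about 0% to 16%. My judgement of 0.5% to 5% as most plausible rests on scales predicting the post-test item no better than they predict the same-day pre-test item (first three rows of the table). At N = 300 that is worth between almost nothing and about 5 points of power.

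The stratification factor is the covariate with the clearest claim, because the design itself uses it and it must be known for every student randomised within strata. It belongs in every model, whatever is decided about the scales.

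**What to change.** Replace the covariate sentence in 11.1 with:

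> For each outcome, covariates will be the corresponding pre-test measure and the randomisation stratum (ever vs never sexually active). The communication-intention model will also include pre-test communication self-efficacy; the condom-intention model will also include pre-test condom self-efficacy, condom attitudes and condom norms. A missing pre-test score, including the outcome's own, will be set to the overall pre-test mean ignoring arm, so that no student with a post-test score is dropped.

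Fix this list before anyone sees outcome data by arm. Filling a missing baseline score with a mean that ignores arm keeps the randomised comparison valid.

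The change costs SAP wording and, beyond the present model, two degrees of freedom for communication intention, four for condom intention and one for each other outcome. No new data are needed.
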